4. TRIAL SUMMARY

Trial Title A Randomised Controlled Trial of the Clinical and Cost

Effectiveness of Low Level Laser in the Management of Oral

Mucositis in Head and Neck Cancer Irradiation

Acronym LiTEFORM

Summary of Trial Design A multicentre blinded randomised controlled trial of low level laser

versus sham low level laser therapy (LLLT) in the prevention and management of oral mucositis in head and neck cancer irradiation

Summary of Participant

Population

Adults (≥18 years) referred for head and neck cancer irradiation

Planned Sample Size 380 adults (190 per arm)

Planned Number of

Sites

Up to 10 sites (including 7 pilot sites)

Intervention Duration 6 weeks after first LLLT

Follow Up Duration 14 months after last LLLT

Planned Trial Period 47 months

Intervention Low Level Laser Therapy (LLLT)

Primary Outcome: OMWQ-HN score at week 6 following start of LLLT treatment.

Primary Objective: To compare the clinical effectiveness and cost effectiveness of LLLT plus

standard care vs standard care alone as measured by the Oral Mucositis Weekly Questionnaire-Head and Neck Cancer (OMWQ-HN) in adult

HNC patients receiving (C)RT.

6. GLOSSARY OF ABREVIATIONS

ABBREVIATION DEF	INITION
------------------	---------

AE Adverse Event

ANCOVA Analysis of covariance

AR Adverse Reaction

ARSAC Administration of Radioactive Substances Advisory Committee

Cl Chief Investigator

Conmeds Concomitant Medications

CRF Case Report Form

(C)RT Chemotherapy/ Radiotherapy

DMC Data Monitoring Committee

eCRF Electronic Case Report Form

EQ-5D-5L EuroQol five dimensions questionnaire

EORTIC QLQ30 European Organization for Research and Treatment of Cancer Quality of

Life Questionnaire

EORTC QLQ C30/H&N

35

EORTC Quality of Life Module for Head and Neck Cancer

GCP Good Clinical Practice

Gy Gray (unit)

HNC Head and Neck Cancer

HRA Health Research Authority

ICF Informed Consent Form

ISF Investigator Site File

ISRCTN International Standard Randomised Controlled Trials Number

LLLT Low Level Laser Therapy

MDT Multi Disciplinary Team meeting

NGT Naso-Gastric Tube

Newcastle CTU Newcastle Clinical Trials Unit

NHS National Health Service

OM Oral mucositis

OMWQ-HN Oral Mucositis Weekly Questionnaire - Head and Neck Cancer

PI Principal Investigator

PIC Participant Identification Centre

PIS Participant Information Sheet

PPI Patient and Public Involvement

QA Quality Assurance

QALY Quality-Adjusted Life Year

QC Quality Control

QOL Quality of Life

R&D Research & Development

RCT Randomised Control Trial

REC Research Ethics Committee

RTOG Radio Therapy Oncology Group

SAE Serious Adverse Event

SAR Serious Adverse Reaction

SDV Source Data Verification

SOP Standard Operating Procedure

SSI Site Specific Information

TMG Trial Management Group

TSC Trial Steering Committee

TMF Trial Master File

USAR Unexpected Serious Adverse Reaction

WHO World Health Organisation

7. BACKGROUND

Around 4000 patients per year in England and Wales [1] undergo chemotherapy or radiotherapy (C)RT for head and neck cancer (HNC). 97% of these patients will develop oral mucositis [2].

Oral mucositis (OM) is a debilitating, painful complication characterised by inflammation of the mucous membranes, erythema and ulceration [3]. The tissue inside the mouth can feel as though it has been burnt, with ulcers developing on the mouth lining, tongue and lips. These ulcers can become infected with bacteria in the mouth. The infection can spread to the blood and other organs (sepsis) which can be life threatening. Thus patients with OM are likely to find that their ability to talk, eat and drink is profoundly affected. Swallowing difficulty (dysphagia) is the major determinant of post treatment quality of life [4].

Over 90% of patients need nutritional support for severe dysphagia during and after (C)RT[5]. Weight loss has been shown to lead to poorer survival, and longer periods without food or drink increase the likelihood of long term dysphagia and dependency on tube feeding [6]. The feeding tube can be inserted through the nose or directly into the stomach. To start the feeding and control pain, patients require hospital admission for several days. Feeding tubes can lead to distress and isolation as patients often do not want to be seen in public with a feeding tube in place. Insertion of feeding tubes has a complication rate of 5-15%, and a mortality rate of around 2% [7]. Long-term tube feeding is an independent predictor of long-term quality of life [5] and increased use of painkillers (analgesics).

Mucositis is an independent risk factor for pharyngo-oesophageal stricture. This is a devastating complication which can develop after HNC radiotherapy. A ring of scarring partially or completely blocks the gullet. This can result in the inability to swallow, aspiration and dependence on a feeding tube [8,9].

OM is a predictable side effect of (C)RT treatment, but current management varies across the UK depending on the funding available. Current treatment for OM includes patient education through reinforcing the importance of good oral hygiene, hydration as well as providing nutritional advice and pain management using analgesics, mouthwashes and coating gels. It is determined by the level of side effects that the patient is experiencing and which drugs are available on local formularies.

Low Level Laser Therapy (LLLT) is another treatment that can reduce the severity of OM. LLLT involves the application of low level light (laser) at the affected tissue to reduce inflammation and improve healing. The light is absorbed into the mitochondria, increasing the activity of the cell and accelerating cell healing as well as inhibiting pain receptors. The effect of the laser depends on the wavelength and density of the light as well as the period of time applied.

The expected benefits of LLLT in the patient population are:

1. Reduced pain and associated requirement for painkillers/pain management

- 2. Improved nutrition throughout treatment
- 3. Less dependence on feeding tubes both short and possibly long term
- 4. Reduced admission to hospital
- 5. Fewer treatment interruptions. Sometimes patients may not feel well enough to attend the hospital for their CRT session. Any treatment gaps allow for tumour repopulation, which may also promote the regrowth of chemotherapy –resistant populations. [10]
- 6. Improved patient quality of life during the treatment period and thereafter, particularly regarding swallowing outcomes but also reducing social isolation as many people avoid public places with a nasogastric tube (NGT) in situ.

8. RATIONALE

There is emerging evidence of the efficacy of LLLT as a treatment for OM, which is the most significant cause of acute morbidity of HNC (C)RT. However, there is inadequate evidence of the effectiveness of LLLT for it to be recommended as standard of care. LLLT remains unavailable to NHS patients undergoing HNC apart from, at the time of writing, a small pilot involving one centre. There is a lack of evidence as to whether LLLT is cost effective and how it is most efficiently delivered.

There are two current trials in France and Spain which do not address these important issues. There are no reported studies of potential long term functional and quality of life benefits for the treatment.

A recent systematic review was conducted by Oberoi et al 2014[11]. This included 18 randomised control trials of LLLT as a treatment for OM. The review concluded that prophylactic (preventative) LLLT reduced severe OM in patients with cancer (RR 0.37, 95% confidence interval (CI) 0.20 to 0.67; P = 0.001). It suggested that future research should identify the optimal characteristics of LLLT and determine feasibility in a clinical setting. If its effectiveness can be evidenced, this therapy would meet the well described but as yet unmet needs of patients during (C)RT. The burden on carers and the NHS would also be reduced.

The incidence of head and neck cancer, oropharyngeal cancer in particular, is rising rapidly. In the UK, oropharyngeal cancer has more than doubled between 1995 and 2006 [12]. In Scotland, oropharyngeal cancer has the fastest rate of increased incidence of any cancer. In the U.S., it is estimated that in 2020 oropharyngeal cancer will be more common than cervical cancer. This group of patients is also younger, with fewer comorbidities, and thus likely to survive longer.

Feedback from patients and the public have included comments of 'I was in agony, I could have given up in two weeks' and 'eating was like putting acid on a fire'. OM can have a lifelong impact on the patient. Potential benefits from LLLT include an improved quality of life in an area that is consistently rated by patients as one of the most problematic and distressing for them. If shown to be effective, LLLT could be implemented into practice. The results from this trial have the potential to change the management of this group of patients in the UK and worldwide.

8.1 Risk Assessment

The laser is being used within the CE (Conformité Européenne) marked indication for reducing pain and inflammation for patients with OM.

Class 3b lasers are potentially harmful to the retina. This hazard can be reduced with the provision of laser glasses from the device manufacturer which must be worn by both the practitioner and the patient whilst the device is in operation. The eye protection can be worn over prescription glasses. The risk of unintended laser irradiation of the eye will also be reduced through the removal and covering of reflective surfaces in the treatment area. The door of the treatment area will be locked and a sign displayed to indicate the use of laser therapy.

Before the treatment starts the operator will ask the patient to report if the light from the laser becomes too hot. If the heat becomes excessive, the laser will be stopped and the probe allowed to cool down.

The laser must not be used over the pregnant uterus, but will only be used in the oral cavity for this trial. Although in line with manufacturer recommendations the laser can be used with caution in pregnant women, women who are known to be pregnant at the time of their treatment, or are planning to become pregnant, will not be eligible to take part in LiTEFORM. Each participating site will follow their standard protocols for (C)RT, which ensure that women of childbearing age are not pregnant whilst undergoing their (C)RT. If a woman is reported to become pregnant during the treatment, LLLT treatment will be stopped immediately. The patient will be followed for the duration of the trial for outcomes unless she withdraws from the trial.

There is some anxiety amongst physicians that if the laser can stimulate healing of normal cells, that it may have a preserving effect on cancer cells. At present the effects of LLLT on tumour behaviour have been inadequately studied. There are a few published in vitro studies. These studies have inconsistent results, which may reflect varying dosimetry and power of the laser. Although there are no case reports of adverse outcomes following LLLT, it remains biologically plausible that LLLT may have an adverse impact on tumour behaviour resulting in poorer outcome and survival. This trial will

aim to address this question by collecting and reporting tumour recurrence and progression during the study period.

9. OBJECTIVES AND OUTCOME MEASURES

The main aim of the study trial is to establish the benefit of LLLT delivered 3 times weekly delivered by trained staff in the management of OM in HNC irradiation.

9.1 Primary Objective

 To compare the clinical effectiveness and cost effectiveness of LLLT plus standard care vs standard care alone as measured by the Oral Mucositis Weekly Questionnaire-Head and Neck Cancer (OMWQ-HN) in adult HNC patients receiving (C)RT.

9.2 Secondary Objective(s)

- Determine the effectiveness of LLLT in preventing severe OM during RT or CRT for HNC as measured by WHO mucositis scores.
- Apply evidence derived from the trial to inform NHS guidance in the use of LLLT for managing OM.
- Investigate the short and long term benefits to patients in terms of dependence on feeding tubes, nutritional status, pain control, admission to hospital, treatment interruptions and swallowing function and quality of life.
- Investigate the long term risks of LLLT (survival, recurrence, disease progression).
- Identify barriers and facilitators to implementing LLLT in routine clinical care through a qualitative process evaluation.

Economic evaluation:

- To compare the total costs, of LLLT and sham LLLT measured at 4 and 14 months, calculated by combining data collected from the eCRF, Health Utilisation and Time and Travel Questionnaires with nationally available unit cost data [13].
- To compare quality-adjusted life years (QALYs) derived from the responses to EQ-5D-5L and EORTC QLQ30 measured at baseline, throughout the trial (week 6 and 4 and 14 months).
- To compare the cost-effectiveness measured in terms of the incremental cost per change (improvement) in OMWQ-HN score recorded between baseline and at week 6 of therapy (as detailed in the statistical primary end point).
- To evaluate incremental cost per QALY of LLLT when compared to standard care (from the

perspective of the NHS and personal and social services to participants and families over 14 months)

Qualitative Sub-study:

 To identify barriers and facilitators to recruitment by interviewing patients, interviewing health professionals, observing launch event and site initiation visits, and audio-recording recruitment consultations.

- To feedback to sites regarding barriers and facilitators that have been identified by developing
 a detailed action plan and site specific feedback.
- To understand practitioners' and site experiences of training in and delivering LLLT and the "fit" of LLLT within the treatment pathway.
- To identify barriers and facilitators to wider implementation of trial findings and LLLT.

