9.3 Outcome Measures

9.3.1 Primary outcome measure

Primary Outcome: OMWQ-HN score at week 6 following start of LLLT treatment.

9.3.2 Secondary outcome measures:

- OMWQ-HN and WHO mucositis scores collected at baseline and weekly during weeks 1-6 of treatment.
- Long term reported health related quality of life as measured by EORTC QLQ C30 (version 3.0),
 EORTC QLQ C30/H&N 35 (EORTC QOL Module for Head and Neck Cancer) and the EQ-5D-5L at baseline, week 6, month 4 and month 14, and MDADI at baseline, week 6, month 4 and month 14.
- Nutritional Parameters as measured by Performance Status Scale's (PSS-HN) collected weekly
 at baseline, weeks 1-6, month 4 and month 14. Recording of weekly weight changes from
 baseline during treatment, the quantity of enteral nutrition consumed, number of days of
 feeding tube in situ.
- Changes in swallowing function measured by the timed water swallow test collected at baseline, week 6 of LLLT month 4 and month 14.
- Pain outcomes as measured by use of analgesics/ topical treatment and pain domain of EQ 5D-5L and OMWQ-HN at randomisation and weekly to week 6 during treatment.

 Safety, specifically adverse events attributed to LLLT and clinical complications notably number of days as inpatient hospital admissions and interruptions in CRT treatment (recorded weekly 1-6 during treatment).

• Clinical outcomes specifically patient survival, quality-adjusted survival recurrence and persistence of disease at 14 months.

Economic outcomes:

- Incremental cost per change in OMWQ-HN score recorded between baseline and at week 6 of therapy and incremental cost per QALY over 14 months
- Quality-adjusted life years based upon EQ-5D-5L [14] and EORTC-8D [15] utility scores measured at baseline, week 6 and 4 and 14 months
- Costs associated with treatment (weeks 0-6) will be collected weekly via the eCRFs
 (e.g. adverse events and use of analgesics)
- Health care utilisation based on responses to Health Utilisation Questionnaire administered at 4 and 14 months (assessing: visits to the GP/walk-in clinic/A&E etc.)
- Participant and family costs collected via the Time and Travel Questionnaire administered at 14 months
- Total costs of LLLT and sham LLLT measured at 4 and 14 months, from the perspective of the NHS and personal and social services to participants and families

Qualitative outcomes as identified through:

- Observations of training
- Interviews with health professionals delivering LLLT

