16.1 Statistical Analysis Plan

The primary analysis of the primary outcome is a comparison of the OMWQ-HN score at 6 weeks following start of RT (+/- 2 weeks) in the two randomised arms. Mean baseline and 6-week scores will be presented (with 95% CI) as well as the mean difference from baseline score. Transformation may be appropriate for non-normally distributed data. The null hypothesis to be tested is H0: mean 6-week score in patients randomised to LLLT = mean 6-week score in patients randomised to sham LLLT. Randomisation is stratified by known clinical confounders of cancer treatment: 1. planned treatment (radiotherapy alone or chemo-radiotherapy 2. Unilateral or bilateral radiotherapy fields.

The size and significance of any treatment effect will be estimated in a multivariable linear regression model adjusting treatment by the stratification factor. Secondary analyses of the primary outcome will adjust the size and significance of any treatment effect by other important baseline clinical covariates (importance assessed through univariate modelling) using multivariable regression and ANCOVA. Underlying assumptions of the regression models and non-linear continuous covariates will be investigated, reported and addressed. A two-sided 5% level of significance will be used.

A sensitivity analysis may be carried out on an imputed dataset, based on multiple imputation methods, to deal with missing data and will be described in the Statistical Analysis Plan, which will be

finalised prior to any analysis of unblinded data.

Comparison of secondary outcome measures has not been powered. As such, descriptive statistics such as means (sd, 95% CI), medians (inter-quartile ranges, range) will be presented by randomised treatment arm for continuous secondary outcome measures, specifically scores, feeding tube days, inpatient admission days, water swallow times. ITT proportions (95% CI) will be calculated and presented for categorical measures.

Time to event summary statistics will be estimated using the method of Kaplan and Meier, and 3, 6 and 12-month estimates (with 95% CI) reported. Differences between 'survival' distributions will be estimated using the hazard ratio (95%CI), unadjusted and adjusted by stratification factors.

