All costs associated with the delivery of the intervention will be included as part of the micro costing exercise based on information detailed in the eCRF. These will be apportioned to patients using standard methodology [32]. Data on resource use, use of services and time away from usual activities as a consequence of the intervention (obtained from the eCRF, Health Utilisation and Time and Travel

Questionnaires) will be combined with trial specific estimates and nationally available data [31] to produce a cost for each trial participant. When appropriate, discounting will be applied to costs and outcomes at UK recommended rates [33]. From these trial participant costs, a mean cost per intervention to the NHS, to the patient and to the NHS and patient combined will be estimated.

Cost-effectiveness analysis & Cost utility analysis

Two types of economic evaluation, cost effectiveness and cost utility will be carried out:

- (1) Cost-effectiveness analysis, based on the incremental cost per change in OMWQ-HN score recorded between baseline and at week 6 of therapy. Mean costs for each randomised arm will be calculated as mean cost per change in OMWQ-HN score. In the cost-effectiveness analysis these will be presented as point estimates of mean incremental costs and effects (improvement in condition specific outcomes (as measured by the OMWQ-HN)) and the incremental cost per change in OMWQ-HN score.
- (2) Cost-utility analysis, based on incremental cost per QALY gained. QALYs will be based upon responses to the responses to the EQ-5D 5L and EORTIC QLQ30 converted generic and disease specific utility scores using available algorithms [34]. The EQ-5D 5L and EORTIC QLQ30 will be completed at scheduled time points (baseline, week 6 and 4 and 14 months). QALYs, based upon EQ-5D 5L and EORTC-8D utility scores will be estimated using the area under the curve approach for each trial participant. Both mean cost and QALYs will be presented for each randomised group and incremental mean costs and QALY calculated along with the incremental cost per QALY gained.

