5.1.2 Secondary analysis of primary outcome

The difference between treatment group means at week 6 will be estimated using analysis of covariance (ANCOVA), adjusting for baseline OMWQ-HN. This will be on a complete case basis for those participants with a score at both baseline and 6 week visit. If the assumptions of the ANCOVA model are satisfied an adjusted mean difference between treatment groups at week 6 with 95% CI will be reported. This analysis is equivalent to analysing the change from baseline adjusted for baseline. The baseline and week 6 OMWQ-HN data will be presented graphically:

Example Figure 5: Spaghetti plot, OMWQ-HN score: change from baseline to week 6

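### Protocol 9.2 attributes the baseline-to-week-6 change in OMWQ-HN to the statistical primary end point, which is the week-6 score, and no section says how the effect in the cost-effectiveness ratio is to be estimated

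*Protocol*

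**What the plan says.** **Economic sections.** Protocol 9.2 sets the effect in the ratio as the change, glossed as an improvement, "in OMWQ-HN score recorded between baseline and at week 6 of therapy (as detailed in the statistical primary end point"). The economic outcomes in Protocol 9.3.2 list "Incremental cost per change in OMWQ-HN score recorded between baseline and at week 6 of therapy and incremental cost per QALY over 14 months". Protocol section 18 describes the cost-effectiveness analysis as "based on the incremental cost per change in OMWQ-HN score recorded between baseline and at week 6 of therapy". None of the three says whether the change is adjusted for baseline.

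**Statistical sections.** Protocol 9.3.1 reads "Primary Outcome: OMWQ-HN score at week 6 following start of LLLT treatment". The null hypothesis in Protocol 16.1 is "mean 6-week score in patients randomised to LLLT = mean 6-week score in patients randomised to sham LLLT". SAP 2.4.1 and 5.1 define the same week-6 outcome, and SAP 5.1.1 reports the unadjusted difference in week-6 means with a 95% confidence interval.

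**Where change appears in the statistical sections.** Protocol 16.1 presents it as a summary beside the scores: "as well as the mean difference from baseline score". SAP 5.1.2 plans a secondary analysis: "The difference between treatment group means at week 6 will be estimated using analysis of covariance (ANCOVA), adjusting for baseline OMWQ-HN". It adds that this gives the same result as analysing change with adjustment for baseline. Neither makes change the primary end point.

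**The concern.** The parenthesis in 9.2 points to an end point that the statistical sections do not contain. Someone following the cross-reference would use the difference in week-6 scores. Someone following section 18 literally could use the difference in raw change, or change adjusted for baseline. The plan allows all three and chooses none.

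The ratio matters because the primary objective (Protocol 9.1, SAP 1.2.1) covers cost-effectiveness as well as clinical effectiveness, both measured by the OMWQ-HN. If the economic analysis used raw change, the report could give one OMWQ-HN effect in the clinical results and another in the ratio and the cost-effectiveness plane. In a trial that closed with 87 participants, chance baseline imbalance could make the two visibly different.

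**Working it through.** **Inputs from the documents.** Meaningful difference 4 points, week-6 SD 10.7, two-sided 5% level, 90% power, 152 evaluable and 190 recruited per arm (Protocol 16.1 and 16.4, SAP 2.6); 87 randomised (SAP 2.6).

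**Assumptions.** The documents give no baseline SD (s0) and no baseline to week-6 correlation (r). I vary s0 over 3, 5, 8 and 10.7, and r over 0.2, 0.35 and 0.5. I take the 87 as 43 and 44 per arm, all evaluable. Missing scores would widen every limit below.

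**The plan's own figure.** n per arm = 2 × (1.96 + 1.2816)² × (10.7/4)² = 150.4, rounded up to 151. The t-based solution is 151.3, rounded up to 152. Then 152/0.80 = 190. The figure reproduces, and it is sized on the SD of the week-6 score, not on the SD of a change.

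**Gap between raw change and the week-6 difference.** The difference in raw change equals the week-6 difference minus the difference in baseline means. Under randomisation that baseline difference has expectation zero, so the two share the same target. In one trial they differ by chance, with 95% limits

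1.96 × s0 × √(1/43 + 1/44) = 1.96 × s0 × 0.2144 = 0.420 × s0.

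**Precision.** With s6 = 10.7:

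- Variance of raw change: s0² + s6² − 2·r·s0·s6 = s6²(1 − r²) + (s0 − r·s6)².
- Residual variance under ANCOVA: s6²(1 − r²).

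The extra term is a square, so raw change is never more precise than ANCOVA, apart from small-sample terms. Raw change is noisier than the unadjusted week-6 score only if r < s0/(2 × 10.7). That threshold is 0.14, 0.23, 0.37 and 0.50 for the four values of s0.

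| Assumed s0 | 95% limits for gap to week-6 difference | Raw-change SE ÷ ANCOVA SE (r = 0.2 / 0.35 / 0.5) | Raw-change SE ÷ week-6 SE (r = 0.2 / 0.35 / 0.5) |
|---|---|---|---|
| 3 | ±1.3 | 1.00 / 1.00 / 1.03 | 0.98 / 0.94 / 0.89 |
| 5 | ±2.1 | 1.04 / 1.01 / 1.00 | 1.02 / 0.94 / 0.87 |
| 8 | ±3.4 | 1.15 / 1.09 / 1.04 | 1.12 / 1.02 / 0.90 |
| 10.7 | ±4.5 | 1.29 / 1.22 / 1.15 | 1.26 / 1.14 / 1.00 |

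As an example, take s0 = 8 and r = 0.2. The raw-change SE is √(64 + 114.49 − 34.24) × 0.2144 = 2.58. The ANCOVA SE is 10.7 × √(1 − 0.04) × 0.2144 = 2.25. The squared ratio is 1.31, equivalent to 31% more patients for the same precision.

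**ANCOVA against the SAP's primary estimate.** These two also differ by chance, with 95% limits 1.96 × r × 10.7 × 0.2144 = 4.50 × r. That is ±0.9, ±1.6 and ±2.25 points for r = 0.2, 0.35 and 0.5.

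**The case against.** The case against making much of this is strong, and most of it stands.

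- **Noise.** A reader might infer that the change measure is noisier than the trial's primary result. The documents do not support that, because they give neither s0 nor r. For s0 of 5 to 10.7, raw change is noisier than the week-6 score in five of nine cells, two of them by under 2%, equal in one and less noisy in three. At s0 = 3 it is less noisy in all three.
- **Size of the gap.** The ±4.5 limit needs a pre-treatment SD as large as the week-6 SD. Baseline is taken before laser therapy (Protocol 13.6), and a patient answering 0 to question 1 scores 0 in total (SAP 5.1). A small baseline SD is therefore plausible.
- **Unadjusted change is not prescribed.** Section 18 names a measure, not an estimator. Analysed with baseline adjustment, change gives exactly the SAP 5.1.2 effect. The supportable criticism is that the estimator is unspecified, not that an inferior one was chosen.
- **The ANCOVA remedy does not match the primary estimate.** SAP 5.1.2 is secondary to 5.1.1, and the SAP already reports both. At s0 = 5 and r = 0.5, ANCOVA can differ from the primary estimate by ±2.25, slightly more than the ±2.1 for raw change.
- **Version.** The protocol supplied is version 2.1. SAP 1.2.2 refers to version 4.0 for the economic objectives, so the wording may already have changed.

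None of this removes the wrong cross-reference in 9.2, or the silence of 9.3.2 and section 18 on baseline adjustment.

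**Conclusion.** The point holds as an error of definition with a modest practical consequence. In protocol version 2.1, section 9.2 misdescribes the primary end point, and the effect in the cost-effectiveness ratio has no stated estimator.

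It should not be read as bias or as a different target, since under randomisation all the candidate estimators share the same expectation. What is at stake is agreement between the clinical and economic results, and some avoidable imprecision if raw change is used. The possible gap to the week-6 difference runs from about ±1.3 to ±4.5 points across assumed baseline SDs of 3 to 10.7, with 87 evaluable participants. The SE is 1.00 to 1.29 times that of ANCOVA for assumed SDs of 5 to 10.7 and correlations of 0.2 to 0.5. These figures apply only if raw change is what would be used, which the documents leave open.

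**What to change.** 1. In Protocol 9.2, delete the cross-reference to the statistical primary end point, or correct it to the week-6 score.
2. In Protocol 9.2, 9.3.2 and section 18, define the incremental effect as the baseline-adjusted difference between arms in week-6 OMWQ-HN (sham minus laser), estimated as in SAP 5.1.2. Use it in the ratio, the cost-effectiveness plane and the acceptability curve.
3. State that this is the SAP's secondary estimate, and show the ratio with the unadjusted SAP 5.1.1 estimate as a sensitivity analysis. ANCOVA needs both a baseline and a week-6 score, so the two may rest on slightly different patients; report both counts.
4. Check first whether the wording persists in protocol version 4.0.

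The cost is a few lines of text and one additional ratio. No new data are needed, and both effect estimates are already planned.
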